## 3.8 Safety Assessment

Unless otherwise specified, all the data collected up to 90 days following the last dose of study drug or the start of a new cancer regimen, whichever is shorter, will be included in the safety summaries. Safety assessments include adverse events, vital signs, clinical laboratory assessments, ECGs, and physical examinations (including ECOG). Safety analyses will be summarized separately for each part as described in section 3.1.4.

#### *3.8.1 Adverse Events (AEs)*

AEs will be captured from signing of informed consent until the Safety Follow-Up Visit up to 90 days after the last dose of study drug or the start of a new cancer regimen, whichever is shorter. All AEs will be coded to system organ class and preferred term using MedDRA version 25.0 or higher. Severity of AEs will be classified using NCI-CTCAE Version 5.0 grading.

Treatment emergent adverse events (TEAEs) are defined as AEs that begin or worsen on or after the start of study.

Treatment related TEAEs are defined as having reasonable causal relationship to study treatment or with missing assessment of the causal relationship.

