### 3 STATISTICAL METHODOLOGY

#### 3.1 General Considerations

##### 3.1.1 *Analysis Day*

Analysis day will be calculated from the date of first dose of study drug. The day of the first dose of the study drug will be Day 1, and the day immediately before Day 1 will be Day -1. There will be no Day 0.

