##### 3.1.5 *Handling of Dropouts and Missing Data*

Unrecorded data values will be recorded as missing. Only recorded (i.e., complete) data values will be used for statistical analyses. In general, invalid, or missing values will not be imputed unless stated otherwise.

If needed, completely or partially missing start and end dates for medical history events, including date of initial diagnosis and last date of last progression for the primary cancer history, will be imputed in a conservative fashion as follows:

Date	Type of Missing Date	Handling of Missing Date
Event Start Date (e.g., YYYY-MM-DD)	Completely missing	No imputation will be applied.
	Only YYYY is available	Use the first day of YYYY to impute the missing month and date parts of the start date
	YYYY and MM are available, but DD is missing	Use the first day of MM to impute the missing date part of the start date
Event End Date (e.g., YYYY-MM-DD)	Completely missing	No imputation will be applied. The event will be considered ongoing at the end of study.
	Only YYYY is available	Use the last day of YYYY to impute the missing month and date parts of the end date
	YYYY and MM are available, but DD is missing	Use the last day of MM to impute the missing date part of the end date

For missing or partial AEs and concomitant medications dates, conservative conventions will be applied to assign the events to corresponding periods. AEs will be considered as treatment-emergent, and the medications will be considered as concomitant if the missing/partial dates cannot definitively exclude the treatment period. Handling incomplete dates (e.g., AE, and concomitant medications dates) are described in Table 7-1 and Table 7-2 from [Appendix A](#).

For patients lost to follow-up or with missing RECIST/iRECIST assessments, censoring rules for efficacy endpoints are defined in section 3.4.

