## 7 APPENDIX

## APPENDIX A: DATE IMPUTATION GUIDELINES

The following date imputation guidelines will apply to adverse events (Table 7-1**Error! Reference source not found.**), and for prior and concomitant medications (Table 7-2**Error! Reference source not found.**).

Table 7-1: Adverse Events date imputation guidelines

AE Start Date	AE Stop Date	Action
Known	Known/Partial/Missing	If start date < study drug start date, then not TEAE If start date ≥ study drug start date, then TEAE
Partial, but the known date components show that it cannot be on or after study drug start date	Known/Partial/Missing	Not TEAE
Partial, could be on or after study drug start date	Known	If stop date < study drug start date, then not TEAE If stop date ≥ study drug start date, then TEAE
	Partial	Impute stop date as latest date (i.e., last day of month if day is unknown or 31-Dec if day and month are unknown), then: If stop date < study drug start date, then not TEAE If stop date ≥ study drug start date, then TEAE
	Missing	Assumed TEAE
Missing	Known	If stop date < study drug start date, then not TEAE If stop date ≥ study drug start date, then TEAE
	Partial	Impute stop date as latest date (i.e., last day of month if day is unknown or 31st December if day and month are unknown), then: If stop date < study drug start date, then not TEAE If stop date ≥ study drug start date, then TEAE
	Missing	Assumed TEAE

Table 7-2: Prior and concomitant medication date imputation guidelines

CM Start Date	CM Stop Date	Action
Known	Known	If stop date < study drug start date, assign as PRIOR If stop date ≥ study drug start date, and start date ≤ end of treatment +90 days, assign as CONCOMITANT
	Partial	Impute stop date as latest date (i.e., last day of month if day unknown or 31-Dec if day and month are unknown), then: If stop date < study drug start date, assign as PRIOR If stop date ≥ study drug start date, and start date ≤ end of treatment +90 days, assign as CONCOMITANT
	Missing	If stop date is missing, then PRIOR will never be assumed or assigned If start date ≤ end of treatment, assign as CONCOMITANT
Partial	Known	Impute start date as earliest date (i.e., first day of month if day unknown or 01-Jan if day and month unknown), then: If stop date < study drug start date, assign as PRIOR If stop date ≥ study drug start date and start date ≤ end of treatment + 90 days, assign as CONCOMITANT

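### The SAP text and Table 7-1 classify an adverse event that starts before dosing and worsens after it in opposite ways, and the text's time anchor is undefined

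*SAP*

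**What the plan says.** SAP 3.8.1 defines TEAEs as "AEs that begin or worsen on or after the start of study". The SAP does not say what event marks the start of study. The same section states that "AEs will be captured from signing of informed consent", so events with onset before dosing are in the database.

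Table 7-1 in SAP Appendix A classifies events against the study drug start date:

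- Known onset date, any stop date: "If start date < study drug start date, then not TEAE"; otherwise it is a TEAE.
- Onset date described as "Partial, but the known date components show that it cannot be on or after study drug start date": not a TEAE, whatever the stop date.
- Onset date ambiguous or missing, with a known or partial stop date: "If stop date < study drug start date, then not TEAE If stop date ≥ study drug start date, then TEAE". If the stop date is also missing, the event is assumed to be a TEAE.

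No row of the table refers to a change in grade. Elsewhere the SAP points to first dose. In 3.1.1, "The day of the first dose of the study drug will be Day 1". In 3.1.2, baseline is the last value before first dose. In 3.1.5, undated events count as treatment-emergent "if the missing/partial dates cannot definitively exclude the treatment period". The protocol uses the term TEAE but gives no time window for it.

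**The concern.** The TEAE flag should isolate what appeared or got worse after exposure. The SAP gives a programmer two instructions that differ on two matters.

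The first is the anchor. Adverse events are captured from consent, and the monotherapy schedule (Protocol Appendix A, Table 20) opens screening at Day -28. Read literally, the text could count screening events that never changed after dosing.

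The second is worsening. The text includes it and the table omits it, so following the table removes events that rose in grade on ANV419.

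The point still applies although the trial stopped after Part 1. SAP section 5 drops only the Part 2, Part 3 and iRECIST analyses. Safety is a secondary objective of Part 1, and most lines of the overview in SAP 3.8.1.1, with their tables by system organ class and preferred term, are built on TEAEs.

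**Working it through.** The plan states no figure here to reproduce. The check applies both rules to the same hypothetical records.

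| Record | SAP 3.8.1 text | Table 7-1 | Agree? |
|---|---|---|---|
| (a) Known onset after consent and before first dose, no later worsening | TEAE if the anchor is consent or enrolment; not TEAE if it is first dose | Not TEAE | Only if the anchor is first dose |
| (b) Known onset after consent and before first dose, grade rises after first dose | TEAE under either anchor | Not TEAE | No |
| (c) Partial onset date that must precede first dose, grade rises after first dose | TEAE under either anchor | Not TEAE | No |
| (d) Known onset on or after first dose | TEAE | TEAE | Yes |
| (e) Ambiguous or missing onset, stop date on or after first dose or also missing | Depends on the unknown onset or worsening date | TEAE, as a conservative assumption | Not a conflict |

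Case (a) depends on how the anchor is read. Sections 3.1.1, 3.1.2 and 3.1.5 and Table 7-1 all point to first dose, and under that reading the conflict in (a) disappears.

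Cases (b) and (c) do not depend on the anchor. Worsening after first dose is also after any earlier start of study, so the text includes the event and the table excludes it. The only escape is that the worsening is entered as a separate record with its own onset date. The protocol and SAP do not require that.

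Comparing (b) with (e) shows an imbalance inside the table. An event with no onset date that ends after first dose is counted. An event known to have begun before dosing that reaches Grade 4 afterwards is not.

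On size, the documents give no count of events with pre-dose onset and post-dose worsening, so the effect cannot be calculated. At maximum enrolment, one reclassified patient moves an arm rate by 1/15 = 6.7 percentage points and the pooled rate by 1/30 = 3.3 points. Those figures apply to any one-patient error, and only where the patient has no other qualifying event in the same table row.

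**The case against.** The strongest reply is that there is only one definition, the one in 3.8.1, and that it includes worsening. Table 7-1 is introduced in 3.1.5 as handling for incomplete dates and is titled as imputation guidance. This does not dispose of the conflict: the table's first row classifies events whose onset date is known, so nothing is imputed there and the row acts as a second rule.

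A second reply is that the gap is narrow, and this largely stands. Under Protocol 7.1, a condition already present at screening goes to medical history and becomes an adverse event only if it changes in severity, frequency or seriousness. Clinically significant abnormal findings present at consent are likewise reported if they significantly worsen. Onset at the time of change is the natural entry for such events, although the documents do not say so. The clear exposure is then an event that first arises between consent and first dose and later worsens. Rules for splitting records may also sit in the separate programming specifications named in SAP section 6.

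A reader might also infer more than the documents support:

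- **That liver toxicity would be hidden.** Drug-related ALT, AST and bilirubin increases each occurred in 6 of 34 patients (18%) in ANV419-001 (Protocol Appendix F). However, SAP 3.8.2 reports shifts to worst post-treatment grade for selected tests, transaminase and bilirubin thresholds, and potential Hy's Law cases, all without the TEAE flag.
- **That every safety table is affected.** The laboratory, vital sign and ECG summaries do not use the flag. The line for events leading to death, the cytokine release syndrome summaries and the listings are not worded as restricted to TEAEs.
- **That screening events would inflate the drug-related counts.** The causality guidance in Protocol 7.1.3 expects a related event to follow dosing. A purely pre-dose event would count as related mainly if causality were missing, which SAP 3.8.1 treats as related.
- **That a primary endpoint is at risk.** Safety was primary only in Part 2, which will not be analysed.

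**Conclusion.** The point holds in a limited form. The conflict over worsening exists under any reading of the anchor, provided that a worsening is not entered as a new record. The conflict over the anchor exists only on the literal wording, which is probably a slip. It would be wrong to conclude that the SAP intends to count unchanged screening events, or that the table counts only events starting after first dose, since ambiguous and missing onset dates are handled conservatively.

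The consequence is confined to the Part 1 TEAE summaries, and its size is unknown. In ANV419-001, 33 of 34 patients (97%) had a related TEAE. If Part 1 is similar, the any-TEAE line would barely move, and any effect would more likely appear in individual preferred terms and in the tables by maximum severity. The one-patient figures of 6.7 and 3.3 points are not estimates of the effect. The SAP should still be corrected, because the rule as written would misclassify events in tables that will be produced.

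**What to change.** Three changes are needed:

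1. In SAP 3.8.1, define a TEAE as an adverse event that starts, or increases in CTCAE grade, on or after the first dose of study drug.
2. In Table 7-1, amend both pre-dose onset rows (known onset date, and partial onset date that must precede first dose) to: not TEAE unless the grade increases on or after first dose.
3. State how a worsening and its date are recorded, either as a new adverse event record or as a dated grade change on the existing record, so that the condition can be programmed.

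The cost is SAP wording and one programming condition, plus a check that the database holds the date of worsening. If the database is already locked, the rule actually applied should be described in the Clinical Study Report, where SAP section 1 requires later deviations to be documented.

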### 3.8.1.1 Overview of TEAEs

An overview of TEAEs will be provided including numbers and percentages of patients (and event counts) with the following:

- Any TEAEs (overall and by maximum severity)
- Any immune related TEAEs (overall and by maximum severity)
- Any ANV419 related TEAEs (overall and by maximum severity)
- Any Pembrolizumab related TEAEs (overall and by maximum severity)
- Any Ipilimumab related TEAEs (overall and by maximum severity)
- Any TEAEs of special interest (overall and by maximum severity)
- Any treatment-emergent serious AEs (TESEAEs)
- Any ANV419 related treatment-emergent serious AEs
- Any TEAEs leading to ANV419 discontinuation
- Any TEAEs leading to Pembrolizumab discontinuation
- Any TEAEs leading to Ipilimumab discontinuation
- Any TEAEs leading to Study discontinuation
- Any TEAEs leading to ANV419 dose reduction
- Any TEAEs leading to Pembrolizumab dose reduction
- Any TEAEs leading to Ipilimumab dose reduction
- Any TEAEs leading to ANV419 dose Interruption
- Any TEAEs leading to Pembrolizumab dose Interruption
- Any TEAEs leading to Ipilimumab dose Interruption
- Any AEs leading to death

The numbers and percentages of patients (and event number) will also be presented by system organ class (SOC) and preferred term (PT) for each of the categories in the overview. For these summaries, patients with multiple adverse events will be counted only once per SOC or PT. Note that Pembrolizumab and Ipilimumab related TEAEs will only be summarized for Combination Dose Finding and Combination Dose expansion parts.

The number of patients experiencing a DLT and the type of DLT (Hematologic or non-hematologic, Pneumonitis, Lab Abnormalities, CRS, Delay longer than 7 days for toxicity or Drug induced liver injury) will be summarized by dose level for the Combination Dose Finding part.

The following categories of Cytokine Release Syndrome adverse events will be summarized:

- Number and percent of patients with any CRS AE, and any CRS event with Grade  $\geq 2$
- Number and percent of patients that experienced diagnostic parameters (Fever, Tachycardia, ...) throughout the CRS event.

- Number and percent of patients with at least one treatment for an CRS event, as well as the number and percent of patients in each treatment category
- Number and percentage of CRS events treated with Corticosteroids and the duration of the Corticosteroids treatment in days
- Number and percentage of CRS events treated with Tocilizumab and the duration of the Tocilizumab treatment in days
- Duration of the CSR events onset time from the last infusion in days computed as date of start of the CSR event – date of last infusion + 1
- Duration of CRS event full recovery in days computed as the date of the full recovery – date of start of the CSR event + 1

A by-patient adverse event data listing will be provided including, but not limited to, verbatim term, preferred term, SOC, NCI CTCAE grade, and relationship to study drug. SAEs, AEs leading to death, and AEs leading to discontinuation from the treatment and from the study will also be listed.

### *3.8.2 Clinical Laboratory Tests*

Blood and urine samples for safety analysis of urinalysis, coagulation, chemistry, serology, endocrinology, and hematology parameters (see [Appendix B](#)) will be obtained as specified in the Schedule of Events in the protocol and processed using local laboratory. For purposes of analysis and reporting, laboratory values will be standardized using International System of Units (SI).

Pregnancy tests (serum or urine) will be performed at pre-specified timepoints.

Clinical laboratory evaluations will be summarized using descriptive statistics for continuous laboratory parameters (coagulation, chemistry, hematology, and endocrinology) for the values and changes from baseline at each scheduled visit. The minimum post-baseline value, maximum post-baseline value, and last post-baseline value will also be presented. Both scheduled and unscheduled post-baseline visits will be considered for the summaries of the last, maximum, and minimum post-baseline values.

Categorical serology and urinalysis parameters will be summarized using number and percentage of patients.

Abnormal laboratory results will be graded according to NCI-CTCAE version 5 as applicable. A shift table, presenting the 2-way frequency tabulation for baseline and the worst post-treatment grade according to the NCI-CTCAE grade will be provided for selected clinical laboratory tests when applicable. Both scheduled and unscheduled post-treatment visits will be considered in tabulation of the worst post-treatment grade.

The number and percentage of patients with laboratory abnormalities will be presented for applicable hematology and serum chemistry laboratory parameters.

Additionally, the number and percentage of patients with the following potentially clinically significant abnormal liver function test will be presented:

- ALT  $\geq 3 \times \text{ULN}$ ,  $\geq 5 \times \text{ULN}$ ,  $\geq 10 \times \text{ULN}$ , and  $\geq 20 \times \text{ULN}$
- AST  $\geq 3 \times \text{ULN}$ ,  $\geq 5 \times \text{ULN}$ ,  $\geq 10 \times \text{ULN}$ , and  $\geq 20 \times \text{ULN}$

- Total bilirubin  $\geq 2 \times \text{ULN}$
- Potential Hy's Law cases: ALT or AST  $> 3 \times \text{ULN}$ , total bilirubin  $\geq 2 \times \text{ULN}$ , and ALP  $< 2 \times \text{ULN}$  at the same visit

Clinical laboratory evaluations will also be listed by patient and abnormal values will be flagged.

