Patients with unresectable or metastatic cutaneus melanoma with measurable disease, whose disease has progressed following at least 1 line of standard of care immunotherapy including an anti-PD-1/ anti-PD-L1 antibody.

Inclusion criteria

Patients who meet all of the following criteria will be eligible to participate in the study:

- 1. Must provide written informed consent for the study;
- 2. Must be able to comply with the Protocol as judged by the Investigator;
- 3. Are ≥18 years of age on day of signing informed consent;
- 4. Have histologically confirmed Stage 3 (unresectable) or Stage 4 (metastatic) CM, as per the American Joint Committee on Cancer staging system, eighth edition;
- 5. Have documented radiological progression on prior systemic therapy;
- 6. Have previously received anti-PD-1/L1 as monotherapy or in combination. A maximum of 2 prior lines of systemic therapy is allowed for BRAF wild-type disease and a maximum of 3 prior lines of systemic therapy is allowed for BRAFV600 positive disease;
 - Note: Adjuvant treatment is considered as a line of therapy only if patient experienced relapse/progression on therapy or within 6 months from adjuvant therapy completion;
- 7. Have measurable disease based on Response Evaluation Criteria in Solid Tumors (RECIST) version 1.1 (hereinafter, RECIST);
- 8. Have a performance status of 0 or 1 on the Eastern Cooperative Oncology Group (ECOG) Performance Status;
- 9. Have adequate organ functions as defined in Table TS4:

Table TS4. Adequate Organ Function Laboratory Values

System	Laboratory Value
Hematological	
ANC	≥1500/µL
Platelets	≥100,000/µL
Hemoglobin	≥9 g/dL or ≥4.96 mmol/L
Renal	
Measured or calculated[1] CrCl (GFR can also be used in place of CrCl)	≥30 mL/min
Hepatic	
Serum total bilirubin OR direct bilirubin	≤1.5 × ULN OR ≤1.5 × ULN for patients with total bilirubin levels >1.5 × ULN; direct bilirubin ≤1.5 × ULN for patients with Gilbert's syndrome
AST (SGOT) or ALT (SGPT)	\leq 2.5 × ULN OR \leq 5 × ULN for patients with liver metastases
Albumin	>2.5 g/dL

Table TS4. Adequate Organ Function Laboratory Values (Continued)

- 1. CrCl should be calculated per Cockcroft-Gault equation.
- ALT = alanine aminotransferase; ANC = absolute neutrophil count; AST = aspartate aminotransferase; CrCl = creatinine clearance; GFR = glomerular filtration rate; SGOT = serum glutamic oxalacetic transaminase; SGPT = serum glutamic pyruvic transaminase; ULN = upper limit of normal.

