### 3.8.3 Vital Signs

Vital signs will be measured as indicated in the Schedule of Events in the protocol. Vital signs will include height (Screening only), weight, systolic and diastolic blood pressure (SBP and DBP), heart rate (HR), respiratory rate, and temperature (presented in Celsius).

Descriptive statistics will be provided for the values and changes from baseline for all vital signs measurements at each scheduled visit. The last, maximum, and minimum post-baseline values will also be presented. Both scheduled and unscheduled visits will be considered for summaries of the last, minimum, and maximum. Vital signs abnormalities will be evaluated using potentially clinically significant (PCS) criteria for minimum and maximum values of SBP, DBP and HR as defined in Table 3-4. The number and proportion of patients with potentially clinically significant changes in vital signs will be presented.

Vital signs assessments will also be listed by patient.

Table 3-4: Potentially clinically significant SBP, DBP and HR

Parameter	PCS criteria
Systolic blood pressure (mmHg)	Minimum SBP $\leq 90$ mmHg
	Minimum SBP decrease from baseline $> 20$ mmHg
	Maximum SBP $\geq 140$ mmHg
	Maximum SBP increase from baseline $> 20$ mmHg
Diastolic blood pressure (mmHg)	Minimum DBP $\leq 60$ mmHg
	Minimum DBP decrease from baseline $> 20$ mmHg
	Maximum DBP $\geq 100$ mmHg
	Maximum DBP increase from baseline $> 20$ mmHg
Heart rate (beats per minute)	Minimum value $\leq 60$ bpm
	Minimum HR decrease from baseline $> 20$ bpm
	Maximum value $\geq 100$ bpm
	Maximum HR increase from baseline $> 20$ bpm

Notes:

- If both the baseline and values of a parameter are beyond the same PCS limit for that parameter, then the value will be considered a PCS value only if it is more extreme (farther from the limit) than was the baseline value.
- If the baseline value for a parameter is missing and the absolute value of a parameter is beyond the PCS limit, then the value will be considered as PCS.
- If the baseline value for a parameter is missing, the change from baseline value will be missing and PCS change criteria will not be assessed.
- The missing category will count the number of patients without any values of the parameter during the period.

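### SAP 3.8.2 counts liver-test abnormalities against fixed ULN multiples with no post-baseline or baseline condition, so patients admitted with ALT/AST of 3 to 5 × ULN or total bilirubin ≥2 × ULN can be counted without any change on drug.

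*SAP*

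**What the plan says.** SAP 3.8.2 announces that "the number and percentage of patients with the following potentially clinically significant abnormal liver function test will be presented". The list has four limits each for ALT and AST (≥3, ≥5, ≥10, ≥20 × ULN), one for total bilirubin (≥2 × ULN), and a combined screen that begins "Potential Hy's Law cases: ALT or AST". The screen requires ALT or AST >3 × ULN, total bilirubin ≥2 × ULN and ALP <2 × ULN at one visit.

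No sentence attached to this list restricts it to values after first dose or refers to baseline. The nearby post-baseline sentence governs other summaries: "Both scheduled and unscheduled post-baseline visits will be considered for the summaries of the last, maximum, and minimum post-baseline values". The CTCAE shift table compares baseline with the worst later grade, but it "will be provided for selected clinical laboratory tests when applicable", and liver tests are not named. SAP 3.8 sets only the end of the safety window, taking in "all the data collected up to 90 days following the last dose of study drug" or up to a new cancer regimen, if that comes sooner.

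Entry limits are in Protocol Table TS4, repeated in Table 9. AST or ALT may be at most 2.5 × ULN, or at most "5 × ULN for patients with liver metastases". The bilirubin row ends "≤1.5 × ULN for patients with total bilirubin levels >1.5 × ULN; direct bilirubin ≤1.5 × ULN for patients with Gilbert's syndrome". Read with its row label, it admits total bilirubin above 1.5 × ULN if direct bilirubin is no more than 1.5 × ULN, and it gives no ceiling for the total.

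For vital signs the SAP does address a patient already beyond a limit. When baseline and later values both lie beyond the same limit, "then the value will be considered a PCS value only if it is more extreme (farther from the limit) than was the baseline value" (SAP 3.8.3, notes to Table 3-4).

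**The concern.** A table of potentially clinically significant liver tests is normally read as showing what happened on treatment. Here the entry limits overlap the reporting limits, so part of a count may describe the patients' condition on arrival.

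The distinction matters for this drug. Protocol Section 5.4.5.1 describes transient transaminase rises as an observed effect of ANV419, and Appendix F, Table 25 reports related ALT and AST increases in 6 of 34 patients each. The arms are small, and SAP 3.8 sends safety summaries to the layout of SAP 3.1.4, which also splits Part 1 by BRAF status. One or two patients who arrive above a limit could make up a visible share of a row. If they fell unevenly between Arms A1 and A2 by chance, the difference could be taken for a dose effect. An entry-level match in the Hy's Law row would be the hardest to interpret.

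The table is still to be produced: SAP Section 5 drops the Part 2, Part 3 and iRECIST analyses, not Part 1 safety.

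**Working it through.** The plan gives no figure to reproduce, so the check is of the rules themselves. Take values that eligibility permits, hold each constant on drug, and apply (a) the limits as written and (b) the same limits with the Table 3-4 condition, under which a value beyond a limit at baseline counts at that limit only if a later value is more extreme.

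Inputs: the limits from SAP 3.8.2; the entry ceilings from Protocol Tables TS4 and 9; the baseline condition from SAP 3.8.3; arm sizes of at most 15 and 30 in total from SAP 2.2.4.

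| Unchanged value (× ULN) | Who can enter with it | Rows met as written | Rows met with Table 3-4 condition |
|---|---|---|---|
| ALT/AST up to 2.5 | any patient | none | none |
| ALT/AST 2.9 | liver metastases | none | none |
| ALT/AST 3, 4 or 4.9 | liver metastases | ≥3 | none |
| ALT/AST 5.0 | liver metastases | ≥3 and ≥5 | none |
| Total bilirubin 1.8 | direct bilirubin ≤1.5 | none | none |
| Total bilirubin 2 or 3 | direct bilirubin ≤1.5 | ≥2 | none |

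The ≥10 and ≥20 rows cannot be reached from an eligible entry value.

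**Hy's Law screen.** Take illustrative entry values, with liver metastases and direct bilirubin ≤1.5 × ULN: ALT 4, total bilirubin 2.2, ALP 1 × ULN. Then 4 > 3, 2.2 ≥ 2 and 1 < 2, so the screen is met before any dose. This needs several uncommon features in one patient.

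**Would the word post-baseline be enough?** No. A patient who enters at 4 × ULN and stays there still has post-baseline values of 4 × ULN and is counted. The restriction would remove only patients whose sole qualifying value came before dosing.

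**Weight of each such patient.** Excess in percentage points = 100 × k/n for k patients in a denominator of n.

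- n = 15: 1/15 = 6.7; 2/15 = 13.3; 3/15 = 20.0.
- n = 30: 1/30 = 3.3; 2/30 = 6.7; 3/30 = 10.0.

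The documents do not give k; the values 1 to 3 are assumed to show the range.

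**The case against.** The SAP never says that pre-dose records enter the count. Elsewhere in 3.8.2 the extreme values are post-baseline, and a programmer might well follow suit. A reader might infer that baseline records are counted by design, but the text is silent and does not support that. The objection stands as far as it goes, although the unchanged patient is counted on either reading.

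The exposure is also narrow. A reader might infer that the whole liver table is inflated. The documents do not support this: ALT/AST is affected only from 3 to 5 × ULN, only with liver metastases, and bilirubin only from 2 × ULN. The Hy's Law match at entry is a rare coincidence, and the row is labelled as potential cases, so it is a screen.

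Other outputs carry baseline information. SAP 3.8.2 provides changes from baseline, maximum post-baseline values, CTCAE grading and listings with abnormal values flagged; TEAEs must begin or worsen on study. With at most 30 patients, a careful reader of the listings could find each carry-over case. This mitigation is real, but it leaves the counts themselves as they are.

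Fixed ULN limits also have precedent here. The drug-induced liver injury note under Protocol Table 15 uses them without baseline adjustment, and the SAP tabulates QTcF >450 ms although entry allows up to 470 ms. Against that, the QTcF list also has increase-from-baseline categories, and the footnotes to Protocol Table 18 (pembrolizumab combination) use multiples of baseline when baseline is abnormal. Fixed limits are a reasonable screen, but they need baseline shown beside them.

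**Conclusion.** The point holds in a limited form. As written, patients stable at an admitted ALT/AST of 3 to 5 × ULN, or at an admitted total bilirubin of 2 × ULN or more, can be counted as liver abnormalities, and rarely as potential Hy's Law cases. Each adds 6.7 points in a full arm of 15 or 3.3 points in 30. This rests on such patients having been enrolled and not worsening, and on reading the bilirubin criterion as a limit on direct bilirubin.

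Two further inferences should be resisted. The number of false cases cannot be estimated, because the documents give neither the frequency of liver metastases nor the distribution of entry values. Nor should the excess be set against the Grade 3 or higher related AST and ALT rates in Protocol Table 1 (2/34 and 1/34): under the protocol's liver grading, Grade 3 transaminase elevation starts above 5 × ULN when baseline is normal, beyond any eligible entry value.

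The table is descriptive, no decision rule uses it, and ORR is untouched. It should still be corrected, because the change is cheap and the SAP already contains a suitable rule.

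**What to change.** In SAP 3.8.2:

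1. Base the counts on post-baseline values from scheduled and unscheduled visits.
2. Apply the Table 3-4 note: a patient already at or beyond a limit at baseline counts at that limit only if a post-baseline value is more extreme than baseline.
3. Add a separate column with the number at or beyond each limit at baseline. It is needed because, under rule 2, even a small fluctuation above baseline is enough to count a patient.
4. Keep every post-baseline potential Hy's Law match in the listing, and flag those that also met the combination at baseline, so that no worsening is hidden.

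A rule that counts only moves into a higher limit category should be avoided. Bilirubin has a single limit, so a rise from 2.1 to 10 × ULN would never be counted, and an ALT rise from 3.1 to 4.9 × ULN would also be lost.

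The cost is SAP wording and table programming. No new data are needed, and the protocol's liver management rules are not touched.
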